4.4.1.5 Other Safety Endpoints

4.4.1.5.1 Pregnancy

This information will not be included in the analysis, but will be listed separately as collected.

4.4.1.5.2 Action Taken

The information will be summarized as collected, including missing observations. No derivation or imputation will be done.

4.4.1.5.3 Seriousness

The information will be summarized as collected. No derivation or imputation will be done.

4.4.1.5.4 Outcome

The information will be summarized as collected. No derivation or imputation will be done.

4.4.1.5.5 Causality

The information will be summarized as collected. Missing causality (relationship) will be handled as described in [Section 5.3.1.2](#). Relationship to study procedure is only presented in the listing.

4.4.1.5.6 AEs Leading to Study Discontinuation

A flag is available in the clinical database for all AEs in order to identify AEs leading to discontinuation.

The items that are counted are:

- Disposition table: A subject who has, on the “Completion at End of Study” form question “What was the participant’s status?” has “Adverse Event” checked
- Safety overview table: A subject who has either on the “Completion at End of Study” form, question “What was the participant’s status?” has “Adverse Event” checked or lists a solicited AE that has “Caused Study Termination” checked that is at least Grade 1 or an unsolicited AE that has “Caused Study Discontinuation” checked that is at least Grade 1 or missing and is within the time period indicated
- System organ class (SOC)/PT frequency table: A solicited AE that has “Caused Study Termination” checked that is at least Grade 1 or an unsolicited AE that has “Caused Study Discontinuation” checked that is at least Grade 1 or missing and is within the time period indicated

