5.2.7.2 Definitive Contraindications

Should a subject experience 1 of the conditions listed below, the Investigator will discontinue vaccination:

- 1) Pregnancy, as indicated by a positive urine test
- 2) Dengvaxia® administered inadvertently during the study (eg, as part of a vaccination campaign)
- 3) An anaphylactic or other significant allergic reaction to the previous dose of vaccine
- 4) Abnormal laboratory parameter of Grade 2 or 3 and assessed by the Investigator as related to the previous dose of vaccine
- 5) Subject deprived of freedom by an administrative or court order, or in an emergency setting, or hospitalized without her/his consent
- 6) Self-reported or suspected congenital or acquired immunodeficiency, except HIV, or receipt of immunosuppressive therapy such as anti-cancer chemotherapy or radiation therapy within the preceding 6 months, or long-term systemic corticosteroids therapy (prednisone or equivalent for more than 2 consecutive weeks within the past 3 months)
- 7) Ongoing clinical AE related to the previous study vaccination, and in the Investigator's opinion, contraindicating further vaccination
- 8) SAE related to the study vaccine following the previous study vaccination
- 9) Confirmed CD4 count < 200 cells/mm³

Subjects will not be withdrawn due to contraindication but will be followed-up for safety. Subjects will not be replaced.

If a female subject who has already received at least one injection becomes pregnant during the study, she will continue to be followed for safety assessments until delivery or until 6 months after the last injection, whichever is the latest. No additional injections will be administered.

Subjects with a definitive contraindication will continue to be followed-up for the study-defined safety and immunogenicity assessments, as applicable.

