5.2.10 Classification of Subjects Who Discontinue the Study

For any subject who discontinues the study prior to completion, the most significant reason for early termination will be checked in the CRB. Reasons are listed below from the most significant to the least significant (refer to the CRF completion instructions for additional details and examples):

Serious Adverse Event	To be used when a subject drops out of or is withdrawn from the study by the Investigator because of the occurrence of an SAE, as defined in Section 9.1.1.1
Adverse Event	To be used when the subject is permanently terminated from the study because of an AE (including an SAE), as defined in Section 9.1.1.1 . This category also applies if the subject experiences a definitive contraindication that is an SAE or AE.
Non Compliance with Protocol	To be used when the Investigator withdraws a subject from the study because of failure to follow the protocol, including when it is retrospectively discovered that a subject did not fulfill the eligibility criteria. The Investigator will provide a comment as to the specific cause of non-compliance.
Lost to Follow-up	To be used when the subject cannot be found or contacted in spite of efforts to locate him/her before the date of his/her planned last visit, as outlined in Section 5.2.9 . The certified letter was sent by the Investigator and returned unsigned, and the subject or parent/guardian did not give any other news and did not come to any following visit.
Protocol Deviation	To be used: 
• In case of significant non-compliance with the protocol (eg, deviation of the Inclusion / Exclusion criteria, non-compliance with time windows, blood sampling, or vaccination refusal, missed injection/treatment, or error in the vaccine/treatment administration)• If the subject experiences a definitive contraindication that is not an SAE or AE• The subject or the parent/guardian signed the certified letter sent by the Investigator but did not give any other news and did not come to any following visit

Withdrawal by Subject To be used:

- When the subject or parent/guardian indicated unwillingness to continue in the study
- When the subject or parent/guardian made the decision to discontinue participation in the study for any personal reason other than an SAE/AE (eg, subject is relocating, inform consent withdrawal, etc.)

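### The SAP's rule for AE discontinuations names only one of the protocol's two AE-type termination reasons, and no per-subject count is defined for AEs that stop vaccination but not study participation

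*SAP*

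**What the plan says.** SAP 4.4.1.5.6 (AEs Leading to Study Discontinuation) opens with the statement that "A flag is available in the clinical database for all AEs in order to identify AEs leading to discontinuation" and gives three counting rules.

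- Disposition table: a subject counts if the end-of-study form, at the participant-status question, "has “Adverse Event” checked".
- Safety overview: the same status, or a solicited AE of at least Grade 1 flagged as causing study termination, or "an unsolicited AE that has “Caused Study Discontinuation” checked that is at least Grade 1 or missing and is within the time period indicated".
- SOC/PT frequency table: the AE-level flags alone, without the status.

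Protocol 5.2.10 says that "the most significant reason for early termination will be checked in the CRB" and ranks the reasons. First comes 'Serious Adverse Event', which applies when the exit, by dropout or withdrawal, is "because of the occurrence of an SAE". Second comes 'Adverse Event', for a subject "permanently terminated from the study because of an AE (including an SAE"). That second reason also covers a definitive contraindication that is itself an AE or SAE.

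Protocol 5.2.7.2 lists the definitive contraindications that end vaccination. Several are AE-based: significant allergic reaction, related Grade 2 or 3 laboratory abnormality, ongoing related clinical AE, related SAE. It then states: "Subjects will not be withdrawn due to contraindication but will be followed-up for safety".

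Protocol 9.1.1.3.2 and 9.1.1.3.3 collect 'Discontinuation of study vaccination' as an action taken, for solicited reactions and for unsolicited AEs. SAP 4.4.1.5.2 says that action taken is summarised as collected. SAP 5.1.1.2 lists action taken among the descriptors for solicited reactions but not for unsolicited AEs.

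**The concern.** The SAP rule and the protocol's discontinuation scheme do not line up in two places.

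First, the protocol offers two AE-type reasons, ranks the SAE reason higher and asks for only one to be checked. A site that follows the ranking codes an SAE exit as 'Serious Adverse Event', and the SAP's status test does not name that value.

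Second, the protocol's stated course for a subject with a serious or limiting related event is to stop the injections, not to leave the study. A table restricted to study discontinuation then answers a narrower question than a reader of a vaccine tolerability report will ask: how many subjects in each arm stopped the series because of an AE? Protocol 5.1.4 treats both kinds of stop as important, since it requires extended follow-up for AEs that end either study participation or vaccination. The SAP carries only the first into a defined count.

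This bears on the per-injection analysis. SAP 5.2.3 analyses safety after each dose, and a subject who stopped after a reaction contributes nothing to later doses. Without a count of such stops by arm and injection, a lower reaction rate after injections 2 and 3 is harder to interpret.

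**Working it through.** **The documents' own design figure.** SAP 5.5 gives a 95% probability of observing an event of 3% true incidence among 100 vaccinees. Check: 1 − 0.97^100 = 0.9524, so it reproduces. The present point does not depend on it.

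**Applying the SAP rules to each route.** The SAP defines an SAE as an unsolicited AE (4.4.1), and protocol 9.1.1.3.3 records for every unsolicited AE, serious or not, whether it caused study discontinuation. The flag route is therefore open to SAEs.

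| Route | Disposition | Overview | SOC/PT |
|---|---|---|---|
| Leaves study for an SAE, coded 'Adverse Event' | counted | counted | counted if flagged and in period |
| Leaves study for an SAE, coded 'Serious Adverse Event', flag checked, in period | not counted | counted | counted |
| As above, but flag unchecked or event out of period | not counted | not counted | not counted |
| Injections stopped for an AE, subject stays in the study (5.2.7.2) | not counted | not counted | not counted |
| Injections stopped for an AE, subject coded as an 'Adverse Event' termination (5.2.10) | counted | counted | counted if flagged and in period |

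The table assumes that the sites use the flag for study discontinuation only, as it is labelled.

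**The period.** SAP 4.4.1.2.3 confines the unsolicited-AE analysis to onset within 28 days of an injection or missing onset. SAP 4.4.1.3 analyses SAEs over several periods, including the whole study. The SAP does not say which period the overview's discontinuation line uses, so row 3 is possible for a late SAE but is not shown to occur.

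**Is the vaccination stop recorded elsewhere?** Yes, as an action taken, with a general summary under SAP 4.4.1.5.2. But 5.1.1.2 leaves action taken out of the unsolicited-AE descriptors, and that class contains all SAEs. No SAP rule turns the item into a count of subjects.

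**Size per subject.** One uncounted subject is 1/100 = 1 percentage point in the vaccine arm and 1/50 = 2 points in the placebo arm. The exact (Clopper-Pearson) 95% intervals show what a shift of one or two subjects does. The counts are illustrative; the documents give no expected number.

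| Count | Estimate | 95% CI |
|---|---|---|
| 0/100 | 0% | 0 to 3.62% |
| 1/100 | 1% | 0.03 to 5.45% |
| 2/100 | 2% | 0.24 to 7.04% |
| 0/50 | 0% | 0 to 7.11% |
| 1/50 | 2% | 0.05 to 10.65% |

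For a zero count the upper limit is 1 − 0.025^(1/n): 1 − 0.025^(1/100) = 3.62% and 1 − 0.025^(1/50) = 7.11%.

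**The case against.** A reader might infer that the SAP loses SAE terminations altogether. The documents do not support that. The overview rule is an either/or, and an SAE that is flagged and in period reaches both the overview and the SOC/PT table. The protocol's 'Adverse Event' reason expressly includes SAEs, so some or all sites may code SAE exits there. The end-of-study form is not in the documents; it may carry a single AE status, or the disposition table may list SAE on its own line. These points stand, and they limit the first part to a mismatch of wording whose effect depends on coding. They do not remove it, because the two protocol reasons overlap and the SAP names one.

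A reader might also infer that AE-related vaccination stops can never count as discontinuations. That does not follow either: protocol 5.2.10 allows an AE-based contraindication to be coded as an 'Adverse Event' termination. What can be said is that 5.2.10 and 5.2.7.2 point in different directions.

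Nor does the mismatch understate the primary endpoints. These are occurrences of reactions, AEs, AESIs, SAEs and hospitalised confirmed dengue (protocol 9.1.1.2); early termination is one of the other derived items. The events that lead to a stop are reported by term and relationship (SAP 5.1.1.2), and SAEs are reported throughout the study.

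Finally, 4.4.1.5.6 is titled for study discontinuation, so leaving out vaccination-only stops fits its title, and the table shells are not available to show that no such row is planned. That is fair. The remaining gap is that no section of the SAP defines the count.

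**Conclusion.** The point holds as a mismatch between SAP 4.4.1.5.6 and the protocol, in two parts.

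1. The disposition rule, and the status part of the overview rule, do not name the protocol's higher-ranked 'Serious Adverse Event' reason. A subject so coded is missed in disposition, and in the overview only when the flag is unchecked or the event is out of period. This rests on the form offering both reasons, as protocol 5.2.10 describes.
2. Subjects whose injections stop for an AE but who remain in follow-up are outside the study-discontinuation count, and no per-subject count of them is defined, although the item is collected and generally summarised.

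The size is 1 point per vaccinee and 2 points per placebo subject left out, and the number is unknown. The consequence is an incomplete or ambiguous discontinuation summary, not a biased primary endpoint. It is worth correcting because it is cheap and because AE-related discontinuation is a standard tolerability summary.

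**What to change.** - In SAP 4.4.1.5.6, count a status of either 'Adverse Event' or 'Serious Adverse Event' in the disposition and overview rules, and state the period that the overview line covers.
- Add a per-subject row, by arm and by injection, for AEs leading to discontinuation of vaccination, derived from the existing action-taken item for solicited and unsolicited events. Add action taken to the unsolicited-AE descriptors in 5.1.1.2.
- Reconcile protocol 5.2.10, which lets an AE-based contraindication be coded as an AE termination, with 5.2.7.2, which does not withdraw subjects for a contraindication. Clarify how the overlapping SAE and AE reasons are to be coded.

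The cost is SAP wording, one derivation and one table row, plus a coding clarification for the sites. No new data are needed. The change should be settled before database lock.

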4.4.1.5.7 Virologically-confirmed Dengue Infection

Virologically-confirmed dengue infection is defined as positive if the positive dengue screen RT-PCR (ie, \geq lower limit of quantification [LLOQ]) result and/or the positive Dengue NS1 enzyme-linked immunosorbent assay (ELISA) result (ie, sample ratio >1) and/or positive Simplexa™ dengue RT-PCR result (ie, “DETECT” for any serotype).

For Dengue NS1 antigen ELISA, sample ratios of <0.5 , ≥ 0.5 to ≤ 1.0 , and >1 will be indicative of negative, equivocal, and positive results, respectively.

4.4.1.5.8 Viremia

The following viremia endpoints will be calculated:

- For all subjects: presence of detectable (\geq lower limit of detection [LLOD]) or quantified (\geq LLOQ) dengue vaccinal viremia (Yes, No, Missing) (by YF RT-PCR method).
- For subjects with a positive YF RT-PCR (ie, \geq LLOD): presence of detectable (\geq LLOD) or quantified (\geq LLOQ) serotype-specific vaccine viremia (Yes, No, Missing) for each of the four serotype (by CYD RT-PCR method).

4.4.1.5.9 CD4 Count

The standardization of CD4 count will be performed using the International System Units if different units appear (eg, if more than one laboratory is involved).

Change in CD4 count after each injection will be calculated in percentages (%) for the derivation of decrease in CD4 count as

$$\frac{CD4\ count\ prior\ to\ vaccination - CD4\ count\ post\ vaccination}{CD4\ count\ prior\ to\ vaccination} \times 100\%$$

The following CD4 count indicators will be derived after each injection:

- Decrease in CD4 count $> 30\%$ post-injection compared to the pre-injection values (ie, percentage change in CD4 count $> 30\%$), not explained by non-adherence to ART and not explained by any other possible etiology: Yes, if the decrease in CD4 count $> 30\%$, otherwise No, when pre- and post-injection CD4 counts are valid and not missing; Missing if either pre- or post-injection count is missing or non-valid.
- Confirmed decrease in CD4 count $> 30\%$ post-injection compared to the pre-injection values (ie, percentage change in CD4 counts $> 30\%$), not explained by non-adherence to ART and not explained by any other possible etiology: Yes if the second test taken 4 weeks after the first (ie, approximately 2 months post-injection) also shows a decrease in CD4 $> 30\%$, otherwise No, if pre- and the two post-injection CD4 counts are valid and not missing; Missing if there are missing or non-valid pre- or post-injection CD4 counts in the first or second test.

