3.2 Trial Plan

An overview of assessments and study vaccinations is provided in Table 3.1 Study procedures.

Each potential subject will sign and date the ICF. In addition to the Screening Visit, all included subjects will attend 8 study visits, will receive 4 follow-up phone calls, and will be contacted 6 months after the last vaccination for a safety follow-up.

Vaccination

All subjects will receive 3 injections of either CYD dengue vaccine or placebo at Day (D) 0, Month (M) 6, and M12.

Blood sampling

A number of immunological (hepatitis B virus antigen [HBsAg], hepatitis C virus [HCV] Abs), hematological (hemoglobin, hematocrit, platelet count, white blood cells count), and biochemical (aspartate aminotransferase [AST], alanine aminotransferase [ALT], urea and creatinine) parameters will be assessed at screening (unless the tests have already been performed as part of routine follow-up within the 4-week time window). The subject's dengue serostatus will be determined by RDT or ELISA during the Screening Visit.

Dengue, YF, and Zika baseline status will be assessed at D0.

Dengue vaccinal viremia will be assessed at D7 and D14 post-Inj 1.

Dengue neutralizing antibody (Ab) levels will be assessed at baseline (V01; prior to Inj 1) and 28 days after each injection.

If no HIV viral load and CD4 count results are available prior to each injection (ie, tests have not been performed within 2 months before injection visit), tests will be performed to ensure that results are available at the time of injection visit.

HIV viral load and CD4 count will be assessed 28 days after each injection. In case an increase in HIV viral load (plasma HIV-1 RNA > 1000 copies/mL 28 days post-injection after having been undetectable [< 50 copies/mL] pre-injection) or a decrease in CD4 count (decrease greater than 30% 28 days post-injection compared to the pre-injection value) is observed, a second blood sample is to be taken 4 weeks later for confirmation, as it is current local practice to confirm abnormal and significant deterioration of HIV-condition related results (20).

Collection of safety data

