Previous exposure to dengue using RDT or dengue ELISA §§	X													
FV status (dengue, YF, and Zika)***		BL1												
Dengue neutralizing Abs***		BL1				BL4				BL5				BL6
Dengue vaccinal viremia			BL2	BL3										
CD4 count and HIV Viral Load†††		†††			BL4†††	†††			BL5†††	†††			BL6†††	

Visit (V) and Phone Call (PC) Number	Scr.*	V01*	V02	V03	V04	V05	PC1	PC2	V06	V07	PC3	PC4	V08	6-month Follow-up†	
Trial Timelines Injection (Inj); Day (D); Month (M)	-D28 to – D0	Inj 1 (D0)	Inj 1 +7D	Inj 1 +14D	Inj 1 +28D	Inj 2 (M6)	Inj 2 +7D	Inj 2 +14D	Inj 2 +28D	Inj 3 (M12)	Inj 3 +7D	Inj 3 +14D	Inj 3 +28D	Last Inj +6 months	
Time Windows (Days)			+3	+3	+14	±20	+3	+3	+14	±20	+3	+3	+14	+30	
Virological confirmation of dengue by NS1 Ag ELISA and/or WT dengue RT-PCR	All acute febrile illness with diagnosis of dengue requiring hospitalization within the first 5 days after fever onset, occurring after the first visit (V01) and until the end of the 6-month safety follow-up														
Injection		Inj. 1				Inj 2				Inj 3					
30-Min. Observation Period – Collection of immediate events		X				X				X					
Injection Site Reactions & Systemic Events Assessment	Solicited injection site reactions will be collected for Days 0–7 after each injection. Solicited systemic reactions will be collected for Days 0–14 after each injection. Unsolicited events will be collected for Days 0–28 after each injection.														
Diary Card (DC)\$\$\$\$		DC1	DC1	DC1	DC2 DC1 DC1	DC3 DC2 DC2			DC4 DC3 DC3	DC5 DC4 DC4			DC5 DC5		
Memory Aid (MA)\$\$\$\$													MA		
Termination Record****													X		
SAEs and Serious AESIs††††	####	SAEs from the first visit (V01) and until the end of the 6-month safety follow-up; AESIs in defined time windows according to the type of AESI													

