- §§ Tests will be performed sequentially. RDT will be performed first, and IgG ELISA will only be performed on subjects who tested negative for RDT. Subjects who previously tested negative by RDT can be re-screened using dengue IgG ELISA.
- *** Blood sample to be collected before vaccine injection.
- ††† Pre-injection HIV viral load and CD4 count will come from routine periodical tests of subjects as per local guidelines. For subjects for whom CD4 count is not part of the routine periodical follow-up as per guidelines, the Investigator will assess CD4 count to ensure that results are available at the time of Visit 1. Likewise, if CD4 count is not available before Inj 2 and Inj 3 (for checking contraindication) the Investigator will assess CD4 count to ensure that results are available at the time of Inj 2 and Inj 3. Pre-injection CD4 count test should be performed within 2 months before the corresponding vaccination visit.
- †††† If an increase in HIV viral load (plasma HIV-1 RNA increase > 1000 copies/mL 28 days post-injection after having been undetectable [< 50 copies/mL] pre-injection) or a decrease in CD4 count (decrease in CD4 count greater than 30% assessed 28 days post-injection compared to pre-injection value), another blood sample is to be taken 4 weeks later for confirmation.
- §§§ DCs are used for the collection of solicited and unsolicited AEs and concomitant medication. DC2 and DC4 are used for the collection of medical events and/or hospitalization and medications at the time of the event in the period between V04 and V05 and V06 and V07, respectively. Each DC is to be reviewed and collected by the site at the following visit. The MA is used for the collection of medical events and/or hospitalization and medications at the time of the event for 6 months after the third injection. The caller will ascertain whether any SAEs occurred since the last contact. During the follow-up period, subjects will be instructed to contact the clinical site if they are hospitalized or experience an AE that might be considered serious.
- **** Termination record will be checked either during a planned study visit or a phone call.

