4.4.1.5.10 HIV viral load

The following HIV viral load indicators will be derived after each injection:

- Increase in HIV viral load: Yes, if plasma HIV-1 RNA < 50 copies/mL pre-injection and > 1000 copies/mL post-injection, not explained by non-adherence to ART and not explained by any other possible etiology, otherwise No, if pre- and post-injection HIV viral load are valid and not missing; Missing if either pre- or post-injection HIV viral load is missing or non-valid.
- Confirmed increase in HIV viral load: Yes, if plasma HIV-1 RNA < 50 copies/mL pre-injection and > 1000 copies/mL post-injection, not explained by non-adherence to ART and not explained by any other possible etiology and a second test taken 4 weeks after the first (ie,

approximately 2 months post-injection) also shows plasma HIV-1 RNA > 1000 copies/mL, otherwise No, if pre- and post-injection HIV viral load are valid and not missing; Missing if there is missing or non-valid pre- or post-injection HIV viral load value in the first or second test.

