4.4.4.3 Duration of the Study

The duration of the study is computed in days as follows: Latest date of all subjects (termination date, last visit date, date of last contact) – earliest date of all subjects (date of visit V01) +1.

5 Statistical Methods and Determination of Sample Size

The statistical analyses will be performed under the responsibility of the Sponsor’s Biostatistics platform using SAS® Version 9.4 software or later. The final analysis will be conducted once the 6-month safety data have been collected and the final database lock has occurred. No statistical adjustment is necessary because no hypotheses will be tested.

For descriptive purposes, the following statistics will be presented:

Table 5.1: Descriptive statistics produced

Baseline characteristics and follow-up description	Categorical data	Number of subjects. Percentage of subjects.
	Continuous data	Mean, standard deviation, quartiles, minimum, and maximum.
Clinical safety results	Categorical data (AEs)	Solicited: Number and percentage (95% CIs) of subjects. Unsolicited: Number and percentage (95% CIs) of subjects, and number of events.
	Categorical data (decrease in CD4 count, increase in HIV viral load, virologically-confirmed dengue case)	Number of subjects Percentage of subjects
Viremia	Categorical data	Number and percentage of subjects with a detectable or quantified viremia (possibly 95% CI of the percentage of the subjects)
	Continuous data	Mean, standard deviation, minimum and maximum (possibly median and quartiles) on quantified viremia data.
Immunogenicity results	Categorical data (cutoff)	Number and percentage (95% CIs) of subjects.
	Continuous data (titer/data)	Log10: Mean and standard deviation. Anti-Log10 (work on Log10 distribution, and anti-Log10 applied): Geometric mean, 95% CI of the geometric mean, quartiles, minimum, and maximum. Graphical representation by Reverse Cumulative Distribution Curve (RCDC).

The confidence interval (CI) for the single proportion will be calculated using the exact binomial method (Clopper-Pearson method, quoted by Newcombe (21), ie, using the inverse of the beta integral with SAS).

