5.2.5 Populations Used in Analyses

The SafAS will be used for the description of clinical safety data. Subjects will be analyzed according to the product they actually received.

The immunogenicity analyses will be performed on the PPAS and will be confirmed on the FAS.

Screened subjects and randomized subjects will be used for various standard population tables including duration of the study, disposition of participants and deviations. Demographic and baseline characteristics will be presented on the PPAS, FAS and SafAS.

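### The SAP codes confirmed CD4 decrease as Missing for nearly every subject whose day-28 count is normal; the parallel HIV-RNA rule overlaps itself, and no denominator is stated

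*SAP*

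**What the plan says.** **CD4, confirmed indicator (SAP 4.4.1.5.9).** Yes requires the second test also to show a fall above 30%. The rest of the rule is "otherwise No, if pre- and the two post-injection CD4 counts are valid and not missing", followed by "Missing if there are missing or non-valid pre- or post-injection CD4 counts in the first or second test".

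**HIV RNA, confirmed indicator (SAP 4.4.1.5.10).** Yes requires both tests above 1000 copies/mL after a pre-injection value below 50. The rule continues "otherwise No, if pre- and post-injection HIV viral load are valid and not missing; Missing if there is missing" and then extends Missing to an absent or non-valid value in either the first or the second test.

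**When the second test exists.** SAP 3.2, with the same text in Protocol 5.1.3, makes it conditional: if day 28 shows an HIV-RNA rise or a CD4 fall beyond the threshold, "a second blood sample is to be taken 4 weeks later for confirmation". The footnote to SAP Table 3.1 agrees: "another blood sample is to be taken 4 weeks later for confirmation". No second sample is planned for anyone else.

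**What is reported.** Table 5.1 lists "Categorical data (decrease in CD4 count, increase in HIV viral load, virologically-confirmed dengue case") with number and percentage of subjects. SAP 5.1.2.2 asks for the first-test and confirmed indicators after each injection. On the population, SAP 5.2.5 says only "The SafAS will be used for the description of clinical safety data". None of these places says how Missing enters the percentage.

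**The concern.** The CD4 derivation asks for data that the sampling plan does not collect. A subject whose count is stable at day 28 clearly has no confirmed decrease, yet cannot be coded No without a second count that nobody was due to draw.

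The HIV-RNA rule fails differently. Its No clause asks only for valid pre- and post-injection values, while its Missing clause also covers an absent second test. A subject without a second test meets both, and that includes a subject with a signal who was never retested.

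With no denominator rule, two programmers following the text can report different percentages from the same data. If Missing is excluded, the figure is roughly the share of retested subjects who were confirmed, not the frequency among injected subjects. In the HIV-RNA case an unresolved signal can be reported as No. Describing CD4 and HIV-RNA changes is a stated secondary objective, and the first-test and confirmed indicators are the only outputs for those markers that SAP 5.1.2.2 and Table 5.1 name.

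**Working it through.** The documents give no expected signal rate, so there is no planned figure on this point to reproduce. The group size of 100 vaccinees comes from SAP 5.5. Its one probability statement does reproduce (1 − 0.97^100 = 0.952, stated as 95%) but plays no part here. All signal counts below are assumptions.

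**Step 1. Apply the rules literally to example values.**

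| Marker | Pre | Day 28 | Second test | Code under the SAP text |
|---|---|---|---|---|
| CD4 | 600 | 580 | none | Missing |
| CD4 | 600 | 400 (−33.3%) | 380 (−36.7%) | Yes |
| CD4 | 600 | 400 (−33.3%) | 580 (−3.3%) | No |
| HIV RNA | 20 | 20 | none | No and Missing |
| HIV RNA | 20 | 5000 | none | No and Missing |
| HIV RNA | 20 | 5000 | 20 | No |

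**Step 2. CD4 percentage.** Take n = 100 with valid pre-injection and day-28 counts, s = 5 first CD4 signals, all retested, and c = 2 confirmed. Let r be the number of subjects with a normal CD4 count who have a second count because the other marker triggered a retest. This is possible because Table 3.1 has one combined sampling row, "CD4 count and HIV Viral Load".

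- Missing excluded: c/(s + r) = 2/5 = 40.0% for r = 0; 2/6 = 33.3% for r = 1; 2/8 = 25.0% for r = 3; 2/10 = 20.0% for r = 5.
- Missing kept: c/n = 2/100 = 2.0% throughout.
- Normal first tests coded Missing: n − s − r = 95, 94, 92 or 90 of 95.

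**Step 3. Other signal counts (r = 0, about half confirmed).**

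| Signals | Confirmed | Coded Missing | Missing excluded | Missing kept |
|---|---|---|---|---|
| 2 | 1 | 98 | 50.0% | 1.0% |
| 5 | 2 | 95 | 40.0% | 2.0% |
| 10 | 5 | 90 | 50.0% | 5.0% |
| 20 | 10 | 80 | 50.0% | 10.0% |

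Protocol 1.3.2 expects no safety signals. With none, and no unplanned second counts, every subject is Missing. Excluding Missing then gives 0/0, where the right answer is 0/100 = 0%.

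**Step 4. HIV-RNA overlap.** Assume n = 100, with 5 signals (2 confirmed, 2 retested and not confirmed, 1 not retested) and 95 normal first tests without a second test.

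- Missing clause takes precedence: Yes 2, No 2, Missing 1 + 95 = 96; percentage of non-missing 2/4 = 50.0%.
- No clause takes precedence: Yes 2, No 2 + 95 + 1 = 98, Missing 0; percentage 2/100 = 2.0%, with the unretested signal counted as No.

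**Step 5. Look for a denominator rule elsewhere.** Missing is excluded for presence of solicited reactions (4.4.1.1.3) and for ongoing reactions (4.4.1.1.7). The serotype tables have their own rule (4.4.2.2). Missing is shown or retained for overall days of occurrence, onset and duration of unsolicited events, and action taken (4.4.1.1.6, 4.4.1.2.3, 4.4.1.2.4, 4.4.1.5.2). Each rule belongs to its own endpoint, and none covers CD4 or HIV RNA.

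**The case against.** The best counter-argument concerns weight. The trial is descriptive, the number of confirmed cases is reported beside any percentage, and the hold criteria in Protocol 5.5 use all included subjects as their denominator. This stands, and it limits the finding.

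On HIV RNA, one can read post-injection in the No clause as covering both tests, since the Missing clause later speaks of a first and a second test. That removes the overlap, but it gives HIV RNA the same defect as CD4: subjects without a signal become Missing. The sentence also sets the post-injection value apart from a second test, which favors the overlapping reading.

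The missing-data rules for onset, duration and action taken describe events already counted, so they are weak guides to a subject-level denominator. The closer precedents exclude Missing. That makes the misleading percentage more likely, not less.

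Two smaller points are fair. The SAP names no No/Missing breakdown as an output for these indicators, so if Missing is kept the reported percentage is about right. The values of r also assume that a retest prompted by one marker measures the other, which the text does not state.

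Finally, the indicator may have been meant only for subjects with a signal. The SAP does not say so, although 4.4.1.5.8 explicitly restricts the serotype-specific viremia endpoint to subjects positive on the YF assay.

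**Conclusion.** The concern holds and should be fixed. The CD4 rule conflicts with the sampling plan and nothing elsewhere in the SAP repairs it. The exceptions are subjects with an unplanned second count or a retest prompted by the other marker, hence nearly every rather than every. The HIV-RNA rule either overlaps or shares the CD4 defect, depending on the reading.

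The size depends on assumed signal counts. With 5 CD4 signals in 100, 2 confirmed and r = 0, the same data give 40.0% or 2.0%; across 2 to 20 signals with about half confirmed, the contrast is 40% to 50% against 1% to 10%. The effect is limited to the confirmed indicators. The first-test indicators need only one post-injection value and are coded coherently; cross-tabulated with the confirmed indicators, they would still identify signals without a retest. Confirmed-case counts, SAE reporting (Protocol 10.7) and the hold rules (Protocol 5.5) are unaffected.

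**What to change.** Use one rule in SAP 4.4.1.5.9 and 4.4.1.5.10, keeping the present thresholds and the qualifier that rules out non-adherence and other causes:

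- **Yes:** the first-test indicator is Yes and a valid retest also meets the threshold.
- **No:** the pre-injection and first post-injection values are valid and the first-test indicator is No; or the first-test indicator is Yes and a valid retest does not meet the threshold.
- **Missing:** only if the pre-injection or first post-injection value is missing or non-valid, or if the first-test indicator is Yes without a valid retest. Show the last group in its own row.

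In Table 5.1 or 5.1.2.2, state the denominator: SafAS subjects with valid pre-injection and first post-injection values for that injection. State also that signals without a valid retest stay in the denominator and are not reported as No.

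Applied to the Step 4 data, this gives Yes 2 (2.0%), No 2 + 95 = 97 (97.0%) and signal without valid retest 1 (1.0%). The confirmed share is then bounded by 2/100 = 2.0% and 3/100 = 3.0%.

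The cost is a few lines of SAP wording and programming. No new data are needed, and no threshold, sampling time or clinical rule changes.
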